## 2.8 Study population

The study population is patients 18 years and older with medically refractory ETD. To be eligible for enrollment in the study the patients must meet all the inclusion criteria and none of the exclusion criteria.

### 2.8.1 Inclusion criteria

Subjects MUST:

1. Be  $\geq 18$  years old
2. Have been diagnosed with ETD for no less than 12 months before enrollment with 3 or more of the following symptoms: ear pain, ear pressure, ringing in the ears, cracking or popping sounds in the ears, muffled hearing, or feeling that ears are clogged or “under water”
3. Have an overall ETDQ-7 score  $\geq 3.0$
4. Have a record of failed medical management for ETD consisting of a minimum of either 4 weeks of daily intranasal steroid spray or 1 completed course of an oral steroid within the 12-month period before enrollment
5. Be a candidate for unilateral or bilateral trans-nasal balloon Eustachian tube dilation using the XprESS device
6. Have a temporal bone CT scan (showing the Eustachian tube) without contrast within 6 months of the enrollment date
7. Be able to read and understand English
8. Be able and willing to provide consent
9. Be willing to comply with the protocol requirements

### 2.8.2 Exclusion criteria

Subjects MUST NOT:

1. Have had any head or neck surgery (eg, adenoidectomy, tonsillectomy) including sinonasal surgery or ear tube placement performed within 3 months before enrollment
2. Require concomitant procedures at the time of study enrollment or procedure
3. Have ear tubes in place (tympanostomy tubes, myringotomy tubes, ventilation tubes, or pressure equalization tubes) or perforation of the tympanic membrane at the time of the study enrollment or procedure (patients with healed tympanic membranes after extrusion of tubes are not excluded)
4. Have patulous Eustachian tubes

5. Have had any previous laser tuboplasty surgery or microdebridement
6. Have temporomandibular joint (TMJ) disorders
7. Have early hydrops (Meniere's disease)
8. Have had head or neck radiation therapy or sinonasal malignancy
9. Have a diagnosis of chronic rhinosinusitis (CRS/RARS) that is uncontrolled
10. Have an immunodeficiency
11. Have craniofacial abnormalities or other anatomical conditions (eg, severely deviated septum, tumors, enlarged adenoids or tonsils, severe turbinate hypertrophy) that would prevent transnasal access of Eustachian tubes
12. Have evidence of internal carotid artery dehiscence or anatomic abnormalities
13. Have uncontrolled allergies
14. Have unmanaged gastroesophageal reflux disease (GERD) or laryngopharyngeal reflux (LPR)
15. Be pregnant at the time of study enrollment or procedure
16. Be currently participating in any other drug or device clinical studies excluding postapproval or marketing registry studies

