## 2.9 Methods and procedures

Study methods and procedures are described below. An overview of the required Phase 2 study assessments at each follow-up visit is provided in **Table 1**. Each subject's follow-up schedule is based on the date of randomization (control arm) or the study procedure (balloon dilation arm and crossover subjects).

Table 1. Phase 2 Study Assessment Schedule

Study evaluation	Baseline Within 60 days of procedure for balloon dilation arm	6-Week crossover evaluation (control arm only) ± 7 days	Procedure Within 60 days of baseline or 6-week crossover evaluation	6-Week post procedure ± 7 days	3-Month post procedure ± 15 days	6-Month post procedure ± 30 days (for 510(k) and publication)	12-Month post procedure ± 45 days (for publication)
Informed consent	✓						
Eligibility assessment	✓	✓					
Demographics/history	✓						
CT scan without contrast	✓ a						
Symptoms/exam	✓	✓		✓	✓	✓	✓
Medications b	✓	✓	✓	✓	✓	✓	✓
Nasal endoscopy	✓	✓		✓	✓	✓	✓
Otoscopy examination	✓	✓		✓	✓	✓	✓
Tympanometry	✓	✓		✓	✓	✓	✓
Valsalva evaluation	✓	✓		✓	✓	✓	✓
EQ-5D questionnaire	✓	✓		✓	✓	✓	✓
ETDQ-7 questionnaire	✓	✓		✓	✓	✓	✓
Ear infection assessment	✓ c			✓	✓	✓	✓

Study evaluation	Baseline Within 60 days of procedure for balloon dilation arm	6-Week crossover evaluation (control arm only) ± 7 days	Procedure Within 60 days of baseline or 6-week crossover evaluation	6-Week post procedure ± 7 days	3-Month post procedure ± 15 days	6-Month post procedure ± 30 days (for 510(k) and publication)	12-Month post procedure ± 45 days (for publication)
Audiologic examination	✓					✓	
Pregnancy test (when applicable)	✓		✓				
Procedure pain			✓ d				
Technical success			✓				
Device malfunction			✓				
Adverse events		✓	✓	✓	✓	✓	✓
Revision dilation or additional surgery				✓	✓	✓	✓
Subject satisfaction				✓	✓	✓	✓

a The eligibility CT scan can be performed within 6 months of enrollment.  
b Only ENT-related medications will be recorded (eg, antibiotics, steroids, allergy treatment, decongestants).  
c At baseline, determine the number of ear infections in the 12-month period before enrollment.  
d The pain scale should be completed before discharge from the index procedure. Subjects treated under general anesthesia are not required to assess procedure pain.

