### 2.9.3 Enrollment

A patient will be considered enrolled in the study after the baseline assessment once all the inclusion/exclusion criteria have been met and at the time of randomization.

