#### 2.9.6 Balloon dilation arm assignment and procedure

Subjects should undergo the balloon dilation procedure within 60 days of the baseline assessment (randomized to balloon dilation) or the 6-week crossover evaluation (crossover subjects). All female subjects of childbearing potential are required to have a negative blood or urine pregnancy test **within 10 days before a balloon dilation procedure**.

Refer to the XprESS Instructions for Use (IFU) for specific instructions on system preparation, subject preparation, device set-up, shaping the device, and detailed treatment procedure for using XprESS to perform Eustachian tube dilation.

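### Three exclusions apply again at the procedure, after randomization, and the plan schedules no 6-week ETDQ-7 for a dilation-arm subject who then cannot be dilated

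*Combined protocol and SAP*

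**What the plan says.** Three criteria in Section 2.8.2, repeated in the Investigational Plan Summary, name the procedure as a second time point:

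- exclusion 2: "Require concomitant procedures at the time of study enrollment or procedure";
- exclusion 3, on ear tubes in place or "perforation of the tympanic membrane at the time of the study enrollment or procedure";
- exclusion 15: "Be pregnant at the time of study enrollment or procedure".

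Section 2.9.3 places enrollment after the baseline assessment, "once all the inclusion/exclusion criteria have been met and at the time of randomization". Section 2.9.6 allows the procedure "within 60 days of the baseline assessment (randomized to balloon dilation) or the 6-week crossover evaluation (crossover subjects"). For women of childbearing potential, who "are required to have a negative blood or urine pregnancy test", that test falls in the 10 days before dilation.

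Section 2.9 says each subject's "follow-up schedule is based on the date of randomization (control arm) or the study procedure (balloon dilation arm and crossover subjects"). Section 2.9.7 gives controls a visit 6 weeks (± 7 days) after randomization and lists only postprocedure visits for the dilation arm. Section 2.9.10 provides a 6-week visit for a subject who was not dilated, but only if the device had been inserted. Section 2.7 leaves out of the data analysis randomized subjects who drop out before receiving their assigned treatment. Section 2.7.2 promises analyses of the primary endpoint that account for missing data, without naming a method.

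**The concern.** An eligibility test applied after randomization, to one arm only, can break the comparability that randomization created. It does least harm when the outcome is still collected, because the subject can then be analyzed in the assigned arm. Here the outcome is not scheduled. A subject randomized to dilation who is found pregnant or with a perforated eardrum before the device is inserted has no procedure date, and so no date from which a 6-week visit can be counted. A control with the same event keeps a visit date fixed by randomization.

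Rewording the analysis set in Section 2.7 would not be enough by itself, because there would be no 6-week score to include. With about 20 subjects per arm, each such subject is 5% of the arm.

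**Working it through.** **1. When and to whom the second test applies.** Enrollment is at randomization (2.9.3) and the procedure comes later (2.9.6), so a test at the procedure is a post-randomization test. Controls reach a procedure only by crossover, after their 6-week evaluation (2.9.5). Up to the primary endpoint, then, only the dilation arm meets the second test.

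**2. Whether a 6-week score exists.**

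| Subject | Anchor for the 6-week visit | ETDQ-7 scheduled? |
|---|---|---|
| Control who perforates or becomes pregnant | Randomization (2.9, 2.9.7) | Yes |
| Dilation arm, device inserted, not dilated | Postprocedure visit (2.9.10) | Yes |
| Dilation arm, stopped before insertion | None | No |

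**3. The plan's own sample size.** Inputs from Section 2.6: changes of -2.15 and -0.85 (difference 1.30), SD 1.3, 1-sided alpha 0.025, power 80%. The exact two-sample t-test has power 78.1% at 16 per arm and 80.7% at 17, so 34 in total reproduces. With 10% attrition, 34/0.90 = 37.8, or 38; the planned minimum of 40 covers it. The sample size is not in dispute.

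**4. Loss of numbers alone.** Let k be the number removed from a dilation arm of 20. No removal rate is given, so k = 1, 2, 3 is an assumption. Under the design assumptions power goes from 86.9% (k = 0) to 86.0%, 85.0%, 83.8%. This is minor.

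**5. Dilution from non-receipt.** Assume the k subjects would have changed like controls (-0.85). The all-randomized difference is [(20 - k)(-2.15) + k(-0.85)]/20 + 0.85:

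- k = 1: (-40.85 - 0.85)/20 + 0.85 = -1.235
- k = 2: (-38.70 - 1.70)/20 + 0.85 = -1.170
- k = 3: (-36.55 - 2.55)/20 + 0.85 = -1.105

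The retained subjects show -1.30. Power with 20 per arm, keeping SD 1.3, is 83.3%, 79.2%, 74.5%.

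**6. What step 5 does not show.** If dilation had no effect, both arms would change by -0.85, removed and retained subjects would be alike, and the bias would be 0. Selection bias needs a further assumption: that those removed would have improved by some amount delta less than those retained. The bias is then k × delta/20. With delta = 1.0 it is 0.05, 0.10, 0.15 points, and the 1-sided type I error is about 3.3%, 4.2%, 5.3% instead of 2.5%. For delta from 0.5 to 2.0 the ranges are 2.9% to 4.2% (k = 1), 3.3% to 6.7% (k = 2) and 3.7% to 10.0% (k = 3). The documents supply neither k nor delta.

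**The case against.** A reader might infer that the plan removes worsening ears from the dilation arm and keeps them in control, so that the result is tilted toward the device. The documents do not carry that far, for four reasons.

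- **Withdrawal is not written.** No section says that a randomized subject who meets one of these criteria at the procedure leaves the study. Section 2.9.9 does not list it among its (non-exhaustive) reasons and asks for reasonable efforts to retain subjects. Section 2.9.2 allows rescheduling, though only for active infection.
- **The only eligibility recheck in Table 1's procedure column is the pregnancy test.** Otoscopy and the eligibility assessment are not ticked there. How exclusions 2 and 3 would be detected is not stated, and nothing ties pregnancy to ear outcome.
- **The asymmetry is not established for tubes or other surgery.** Sections 2.9.5 and 2.9.6 bar controls from surgery during the 6 weeks, and Section 2.7 also drops controls who leave before completing that period. The documents do not say that a control who received tubes would be analyzed. The contrast is clear only for perforation and pregnancy.
- **Analysis is not powerless.** A baseline ETDQ-7 exists and Section 2.7.2 commits to handling missing data, so it would be too strong to say that nothing could be done afterwards.

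All four stand, and they limit the claim. They do not close the gap: no section keeps such a subject in follow-up, none gives a date for the missing score, and Section 2.7.2 names neither a method nor a population.

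**Conclusion.** The point holds as a gap in the schedule and the analysis rule. After randomization, a dilation-arm subject who meets exclusion 2, 3 or 15 before device insertion has no scheduled 6-week ETDQ-7 and no stated place in the primary analysis, while a control who perforates or becomes pregnant is still assessed.

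Its size is conditional. With 1, 2 or 3 of 20 not dilated and changing like controls, the all-randomized difference would be smaller than the retained-subject difference by 0.065, 0.130 or 0.195 points. Dividing -1.30 by the diluted values gives ratios of 1.05, 1.11 and 1.18, which might be read as a bias of 5%, 11% or 18% in favor of dilation. They are the gap between two estimands and imply no bias under the null. The type I error figures do describe selection bias, but rest wholly on an assumed worse prognosis. The incidence is unknown and may be zero, and 3 of 20 (15%) exceeds the plan's own 10% attrition allowance. The change is worth making because it is cheap and must be in place before the visits occur.

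**What to change.** 1. In Section 2.8.2, state that after randomization these three criteria decide only whether the procedure goes ahead and do not end study participation.
2. In Section 2.9.7 and Table 1, schedule an ETDQ-7 and adverse event check 6 weeks after randomization for every dilation-arm subject not yet dilated by then. If a subject is found undilatable only after that window, take them at the time of that decision. The second limb is needed: 6 weeks ± 7 days is day 35 to 49, the procedure may be as late as day 60 after baseline, and a subject randomized on the baseline day and stopped on day 50 to 60 would already be past the window. State which score is used if both exist.
3. In Section 2.7, include these subjects, as randomized, in an all-randomized analysis of the primary endpoint. Without this the new score would enter no analysis.

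The rule on who may be dilated is unchanged. The cost is a few sentences, one questionnaire and adverse event check for a few subjects, and a slightly smaller expected difference.

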## 2.9 Methods and procedures

Study methods and procedures are described below. An overview of the required Phase 2 study assessments at each follow-up visit is provided in **Table 1**. Each subject's follow-up schedule is based on the date of randomization (control arm) or the study procedure (balloon dilation arm and crossover subjects).

Table 1. Phase 2 Study Assessment Schedule

Study evaluation	Baseline Within 60 days of procedure for balloon dilation arm	6-Week crossover evaluation (control arm only) ± 7 days	Procedure Within 60 days of baseline or 6-week crossover evaluation	6-Week post procedure ± 7 days	3-Month post procedure ± 15 days	6-Month post procedure ± 30 days (for 510(k) and publication)	12-Month post procedure ± 45 days (for publication)
Informed consent	✓						
Eligibility assessment	✓	✓					
Demographics/history	✓						
CT scan without contrast	✓ a						
Symptoms/exam	✓	✓		✓	✓	✓	✓
Medications b	✓	✓	✓	✓	✓	✓	✓
Nasal endoscopy	✓	✓		✓	✓	✓	✓
Otoscopy examination	✓	✓		✓	✓	✓	✓
Tympanometry	✓	✓		✓	✓	✓	✓
Valsalva evaluation	✓	✓		✓	✓	✓	✓
EQ-5D questionnaire	✓	✓		✓	✓	✓	✓
ETDQ-7 questionnaire	✓	✓		✓	✓	✓	✓
Ear infection assessment	✓ c			✓	✓	✓	✓

Study evaluation	Baseline Within 60 days of procedure for balloon dilation arm	6-Week crossover evaluation (control arm only) ± 7 days	Procedure Within 60 days of baseline or 6-week crossover evaluation	6-Week post procedure ± 7 days	3-Month post procedure ± 15 days	6-Month post procedure ± 30 days (for 510(k) and publication)	12-Month post procedure ± 45 days (for publication)
Audiologic examination	✓					✓	
Pregnancy test (when applicable)	✓		✓				
Procedure pain			✓ d				
Technical success			✓				
Device malfunction			✓				
Adverse events		✓	✓	✓	✓	✓	✓
Revision dilation or additional surgery				✓	✓	✓	✓
Subject satisfaction				✓	✓	✓	✓

a The eligibility CT scan can be performed within 6 months of enrollment.  
b Only ENT-related medications will be recorded (eg, antibiotics, steroids, allergy treatment, decongestants).  
c At baseline, determine the number of ear infections in the 12-month period before enrollment.  
d The pain scale should be completed before discharge from the index procedure. Subjects treated under general anesthesia are not required to assess procedure pain.

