## 2.3 Study endpoints

### 2.3.1 Primary endpoints

The following measures will be collected as the primary endpoints:

- Comparison of mean change in overall ETDQ-7 score from baseline to 6 weeks between balloon dilation arm and control arm
- Complication rate

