## 2.6 Sample size estimation

The sample size was calculated using PASS, Inequality Tests for Two Means (2-sample t-test) to test for superiority of improvement of ETDQ-7 scores at 6 weeks and was based on the following assumptions:

- Significance level (1-sided alpha) = 0.025
- Power = 80%
- Mean change in overall ETDQ-7 score in the balloon dilation group = -2.15
- Mean change in overall ETDQ-7 score in control group = -0.85
- Common standard deviation for both groups = 1.3

Under the assumptions outlined above, a total sample size of 34 randomized subjects (17 per arm) is adequate to test this hypothesis. To account for up to 10% attrition, a minimum of 40 subjects will be enrolled in Phase 2 of the study.

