### 2.9.2 Baseline visit

All candidates for the study will have the following baseline clinical evaluations done **before enrollment and randomization**:

- Informed consent signed
- Baseline medical history, demographics, symptoms, and medication history in the 12-month period before enrollment
- Eligibility assessment: subjects meet all inclusion and no exclusion criteria.
- Nasal endoscopy
- Otoscopy examination
- Tympanometry
- Valsalva evaluation

- Assessment of ear infections over the 12-month period before enrollment
- Audiologic examination including a pure tone auditory (PTA) test
- EQ-5D and ETDQ-7 QOL questionnaires (completed by the study subject)
- Pregnancy test for female subjects of childbearing potential

The results of all baseline evaluations will be documented on the appropriate Case Report Forms (CRFs).

For subjects undergoing balloon dilation, preprocedure antibiotics and steroids may be prescribed at the discretion of the study physician. Medications may be prescribed to treat active infections and procedures may be rescheduled until active infections resolve.

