#### 2.9.7 Follow-up visits

Subjects randomized to the control arm are scheduled for a follow-up visit at 6 weeks ( $\pm 7$  days) after their randomization. At this visit, control subjects will be evaluated and if their ETD symptoms persist (defined as overall ETDQ-7 score  $\geq 3$  or change  $< 0.4$ ), the subjects are eligible for crossover to balloon dilation treatment. Subjects who do not have persistent ETD symptoms are exited from the study after completion of this visit.

Subjects randomized to balloon dilation and crossover subjects are scheduled for the following postprocedure follow-up visits (window):

- 6-Week ( $\pm 7$  days)
- 3-Month ( $\pm 15$  days)
- 6-Month ( $\pm 30$  days)
- 12-Month ( $\pm 45$  days)

The following assessments are required at all follow-up visits:

- Symptom assessment
- Nasal endoscopy examination
- Otoscopy examination

- Tympanogram
- Valsalva evaluation
- Medication use since last study visit
- Ear infections since last study visit
- Revision dilation or additional surgery
- Subject satisfaction
- EQ-5D
- ETDQ-7
- Adverse events

In addition to the assessments noted above, an **audiologic examination is required at the 6-month visit.**

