#### 2.10.1 Primary and secondary endpoint assessments

##### *Mean change in overall ETDQ-7 score*

The Eustachian Tube Dysfunction Questionnaire (ETDQ-7) is a standardized, 7-item questionnaire designed to assess quality of life associated with Eustachian tube dysfunction. The 7 dimensions of the questionnaire are pressure, pain, feeling clogged, cold/sinusitis problems, crackling/popping, ringing, and feeling muffled. Each item is assessed on a 1 (no problem) to 7 (severe problem) scale and an overall score, which is the mean of the 7 dimension scores, is calculated. The questionnaire is designed to be self-completed by the subject. ETDQ-7 questionnaires will be completed at baseline and at all study visits. Changes in overall ETDQ-7 scores will be based on the mean change between the baseline assessment (or 6-week crossover

evaluation for crossover subjects) and each follow-up assessment. Standard treatment effect size may also be calculated for the mean overall ETDQ-7 score. The ETDQ-7 CRF may be considered a source document if completed directly by the subject on the CRF.

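### The primary ETDQ-7 change covers a longer interval in the dilation arm than in controls, because the wait for the procedure sits inside the change score in one arm only

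*Combined protocol and SAP*

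**What the plan says.** All references are to the combined protocol and SAP.

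- **Endpoint.** Section 2.3.1: "Comparison of mean change in overall ETDQ-7 score from baseline to 6 weeks between balloon dilation arm and control arm". Section 2.5 tests it with a 1-sided Student's t-test at 0.025.
- **Visit clocks.** Section 2.9: "Each subject's follow-up schedule is based on the date of randomization (control arm) or the study procedure (balloon dilation arm and crossover subjects". Table 1 gives the control visit as "6-Week crossover evaluation (control arm only) ± 7 days". In Section 2.9.7, "Subjects randomized to the control arm are scheduled for a follow-up visit at 6 weeks", with the same 7-day tolerance, counted from randomization. The dilation arm's visit is 6 weeks, again within 7 days either way, after the procedure.
- **Time to procedure.** Section 2.9.6: "Subjects should undergo the balloon dilation procedure within 60 days of the baseline assessment (randomized to balloon dilation". Section 2.9.2 adds that "procedures may be rescheduled until active infections resolve".
- **Reference score.** Section 2.10.1: "Changes in overall ETDQ-7 scores will be based on the mean change between the baseline assessment". Only crossover subjects get a new reference score. Section 2.9.2 places baseline before randomization in both arms. Table 1 has no ETDQ-7 at the procedure visit.
- **Expected control change.** Section 2.6: "Mean change in overall ETDQ-7 score in control group = -0.85".
- **Allowance for elapsed time.** Sections 2.5 and 2.7 to 2.7.2 contain neither an adjustment nor a sensitivity analysis for it.

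**The concern.** The endpoint reads as one interval applied to both arms, but the schedule produces two. A control subject's change ends about 6 weeks after randomization. A dilation subject's change ends about 6 weeks after the procedure, and still starts at the pre-randomization baseline. Whatever happens to symptoms between randomization and the procedure, with no device yet used, is therefore credited to the dilation arm and has no counterpart in controls.

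The wait is created by the assignment itself, so randomization does not balance it. It also cannot be removed cleanly afterward: the wait exists in one arm only, and no score is taken on the procedure day.

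This comparison is the study's only randomized efficacy test, and it supports an application for a new indication (Sections 1.2 and 2.5). If symptoms keep improving after 6 weeks without dilation, the longer interval alone moves the result in the direction the test looks for. Drugs given around the procedure are taken here as part of the strategy being compared.

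**Working it through.** **1. The plan's own figure.** Section 2.6 gives mean changes of -2.15 and -0.85 (difference 1.3), SD 1.3, 1-sided alpha 0.025 and power 80%. For a two-sample t-test the noncentrality is 1.3 / (1.3 × √(2/17)) = 2.92 at 17 per arm, which gives 80.7% power; 16 per arm gives 78.1%. The stated 17 per arm is reproduced.

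**2. Intervals, if randomization is on the baseline day.**

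| Arm | Calculation (days) | Baseline to primary score |
|---|---|---|
| Control | 42 ± 7 | 35–49 days |
| Dilation | (0 to 60) + (42 ± 7) | 35–109 days |

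**3. Effect of a gap between baseline and randomization.** No limit on this gap is stated. A gap of g days makes the control span 35 + g to 49 + g days. The 60-day limit runs from baseline, so the possible one-arm wait becomes 60 − g days. With g = 14, controls span 49–63 days and the wait can still reach 46 days. The asymmetry shrinks but does not disappear.

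**4. Size of the shift.** The documents give neither the mean wait nor the course of symptoms after week 6. Assumed here: a mean wait of 14 to 30 days, and continued improvement at a fraction f of the planned pace.

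- Planned pace: 0.85 / 42 = 0.0202 points per day.
- Shift = f × 0.0202 × mean wait.
- f = 0 (improvement has stopped): shift 0.
- f = 0.25, 14 days: 0.25 × 0.0202 × 14 = 0.07 points, 5% of the planned 1.3.
- f = 0.25, 30 days: 0.25 × 0.0202 × 30 = 0.15 points, 12% of 1.3.

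**5. Chance of a significant test when dilation has no effect.** Noncentrality = shift / (1.3 × √(2/n)), 1-sided 0.025, at quarter pace.

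| Mean wait | Shift | 17 per arm | 20 per arm |
|---|---|---|---|
| none | 0 | 2.5% | 2.5% |
| 14 days | 0.07 | 3.5% | 3.7% |
| 30 days | 0.15 | 5.2% | 5.5% |

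**6. A different assumed course.** Suppose improvement levels off with a 21-day half-life and is set to 0.85 at day 42. The eventual change is 0.85 / 0.75 = 1.13. The extra change is about 0.10 points by day 56 and 0.18 by day 72, and the error is 4.2%–5.8% at 17 per arm. That is the same order as step 5.

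**The case against.** The strongest defense is that each arm is scored 6 weeks after its assigned management begins: randomization for continued therapy, the procedure for dilation. Time since treatment is then matched at 35–49 days. Because Section 2.9.8 says healing can take up to 3 months, scoring dilation subjects from randomization would catch some of them too early. This is a fair reason for the dilation clock, and it stands. It does not match the interval analyzed, because the change starts at baseline and not at the procedure.

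The second defense is that the drift may be nil. Entry requires ETD diagnosed for at least 12 months, failed medical management and a score of at least 3.0 (Section 2.8.1). Part of the expected -0.85 may be regression to the mean, which does not grow with time. This also stands, and is why the lower bound is zero.

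Two stronger readings are tempting.

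- **That the plan's own figures show a bias toward the device.** Section 2.6 gives one control value, at 6 weeks, and says nothing about what follows. The direction favors dilation only if improvement continues.
- **That control improvement runs on at its full pace, so the error rate is several times nominal.** Full pace is 0.0202 × 365 = 7.4 points a year on a scale with a 6-point range (1 to 7), in people who still score at least 3.0 after a year or more of disease. Figures built on it are not evidence about this trial. Half pace, 3.7 points a year, is also hard to reconcile with the population.

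Finally, 109 days is the limit of the windows, not an expected value.

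**Conclusion.** The mismatch is established by the text: the wait for the procedure lies inside the primary change in the dilation arm only, and the analysis does not allow for it. The spans of 35–49 and 35–109 days hold when baseline and randomization coincide; a gap narrows the difference without closing it.

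The consequence is not established. It is nothing if control improvement is complete by 6 weeks. It is about 0.07–0.15 points, with a 1-sided error of about 3.5%–5.5% instead of 2.5%, if improvement continues at a quarter of the planned pace and the mean wait is 14–30 days. Both of those inputs are assumptions. A reader should not conclude that the 0.025 level fails, only that the design does not protect it against drift during the wait. The point is worth acting on because prevention is cheap and later repair is not clean.

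**What to change.** **Main change**

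1. Section 2.9.4: before the center requests the assignment, record for every Phase 2 subject a planned procedure date no later than 21 days after randomization.
2. Sections 2.9.5 and 2.9.7 and Table 1: take the control 6-week ETDQ-7 at 42 ± 7 days after that planned date. Keep the dilation arm's primary score at 42 ± 7 days after the procedure when it takes place on time or nearly so. Controls, and dilation subjects treated on schedule, then span 35–70 days from randomization (0–21 plus 35–49).
3. Sections 2.1, 2.3.1 and 2.5: restate the endpoint as the change to 6 weeks after the planned (control) or actual (dilation) procedure date.
4. Section 2.7: report days from baseline to primary score by arm, and add a sensitivity analysis restricted to subjects with short waits. This is needed because slipped procedures leave a residual imbalance. An average slip of 7 days, for example, leaves 0.25 × 0.0202 × 7 = 0.04 points at quarter pace. Actual waits arise after assignment and in one arm, so this analysis is supportive only.

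The t-test, alpha and sample size do not change.

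**Simpler fallback.** Leave the control clock alone and, for subjects randomized to dilation, replace the 60-day limit with a procedure within 14 days of randomization. The mean shift at quarter pace is then at most 0.07 points.

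**Cost.** The main change needs one extra date on the Randomization Enrollment CRF and procedure slots within 21 days. Controls may wait up to 21 days longer for crossover, which adds some dropout risk against the 10% allowance in Section 2.6. The fallback avoids the longer control wait but demands tighter procedure scheduling.
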